- [FDA Diversity Guidance](#)

This study will recruit a sample of 30 skeletally mature male and female participants between the ages of 18 and 40 that have undergone arthroscopic ACL reconstruction with partial meniscectomy or meniscal repair. Participants will be recruited from the University of Kentucky's Department of Orthopaedic Surgery & Sports Medicine clinical patient population.

Complete subject inclusion and exclusion criteria are as follows, and patients will not be excluded on the basis of sex, race, or ethnicity:

Inclusion Criteria:

1. Written consent to participate in the study
2. Male or female greater than or equal to 18 years of age and less than 99 years of age
3. Has undergone arthroscopic ACL reconstruction with partial meniscectomy or meniscal repair in the past 4 weeks
4. Ambulatory and in good general health
5. Willing and able to comply with the study procedures and visit schedules and able to follow verbal and written instructions.
6. Willing to abstain from use of protocol-restricted medications during the study
7. Females and males who have reproductive potential: Must use highly effective contraception for at least 1 month prior to the study injection and agreement to use such a method during study participation (18 weeks; 8 to 26 weeks after surgery)
8. Demonstrate persistent inflammation defined as either synovial fluid IL-1alpha concentration >= 5 pg/mL at the time of surgery

Exclusion Criteria:

1. Known allergic reactions to components of the extended-release triamcinolone acetonide (Zilretta®)
2. Reactive arthritis, rheumatoid arthritis, psoriatic arthritis, ankylosing spondylitis, or arthritis associated with inflammatory bowel disease
3. History of infection in either knee joint
4. Clinical signs and symptoms of active knee infection or crystal disease in either knee within 1 month of Screening
5. Other surgery or arthroscopy of either knee within 6 months of Screening
6. Intraarticular treatment of any joint with any of the following agents within six (6) months of Screening: any corticosteroid preparation or any biologic agent (e.g., platelet rich plasma (PRP) injection, stem cells, prolotherapy, amniotic fluid injection; investigational or marketed).
7. Intraarticular treatment in either knee with hyaluronic acid (investigational or marketed) within 6 months of Screening
8. Parenteral or oral corticosteroids (investigational or marketed) within 3 months of Screening

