- *Research Repositories*: If the purpose of this submission is to establish a Research Repository (bank, registry) and the material you plan to collect is already available from a commercial supplier, clinical lab, or established IRB approved research repository, provide scientific justification for establishing an additional repository collecting duplicate material. Describe the repository design and operating procedures. For relevant information to include, see the [UK Research Biospecimen Bank Guidance](#) or the [UK Research Registry Guidance](#).

We will perform a Phase 2a, double-blind, placebo-controlled, randomized controlled trial to determine if a long-acting anti-inflammatory agent (extended-release triamcinolone acetonide) lessens progressive changes in bony shape, improves patient-reported outcomes, and/or reduces biomarkers of cartilage degradation when compared to placebo (saline). The single-site study is driven by the three guiding hypotheses:

Hypothesis 1: The shape changes of the femoral condyle between 8 weeks and 6 months after surgery will be significantly lower for patients treated with extended-release triamcinolone acetonide than the placebo group.

Hypothesis 2: Changes in patient reported-outcomes between eight and 6 months after surgery will be significantly greater for those treated with long-duration anti-inflammatory injections than the placebo group.

Hypothesis 3: Changes in a urinary biomarker of cartilage breakdown (uCTXII) between eight and 6 months after surgery will be significantly lower for those treated with long-duration anti-inflammatory injections than the placebo group.

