- Caucasian patients account for 84% of our knee OA patient population; however, we take the inclusion of minorities very seriously. In a recently completed clinical trial of ACL reconstructed patients, our successful enrollment strategies have resulted in a greater representation of minorities than the general patient population for our area (29% vs. 16%). We aim to meet or exceed these proportions in the proposed study and will approach all eligible minority patients to ensure that at least 25% are non-white.
- Vulnerable populations including pregnant women, children, and prisoners will not be enrolled in this study.
- To promote retention, patients will be compensated \$50 for completing Visit 2 (fluid collected at the time of surgery), and if they qualify for the study injection, participants will receive \$75 for each of the 2 study visits that involve MRI scans. Compensation will be mailed to the participant by check within two weeks after they have completed study visits 2, 3, and 4. If they choose to withdraw early, or do not attend all study visits, payment will be prorated. Participants could earn up to \$200 for participation in this study. No advertisements will be used for this study.

Attachments

Research Procedures

Describe how the research will be conducted.

- What experience will study participants have?
- What will study participants be expected to do?
- How long will the study last?
- Outline the schedule and timing of study procedures.
- Provide visit-by-visit listing of all procedures that will take place.
- Identify all procedures that will be carried out with each group of participants.
- Describe deception and debrief procedures if deception is involved.

Differentiate between procedures that involve standard/routine clinical care and those that will be performed specifically for this research project. List medications that are explicitly forbidden or permitted during study participation.

EFFICACY ASSESSMENTS

PRIMARY OBJECTIVE

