Determine if extended-release triamcinolone acetonide treatment alters progressive changes in bone shape after ACL reconstruction. The bone area of the medial femoral condyl has been shown to increase within the first few months after ACL reconstruction. This is clinically meaningful as similiary bony changes have been previously associated with progressive OA and within 6 months of ACL reconstruction correlated with subsequent patient-reported outcomes and MRI markers of cartilage quality at 3 years. All subjects will undergo MRI examination prior to undergoing the study injection at Visit 3 and again at Visit 4. Sagittal and axial MRI images will be acquired with the knee in full extension using a 3.0-T MRI scanner and an 1Tx/15Rx phased array knee coil. Sagittal and axial T1-weighted spin echo images (FSE) will be acquired to allow semi-quantitative analysis at the conclusion of the study. These sequences will be followed by a sagittal high-resolution 3D dual echo steady state (DESS) sequence for cartilage segmentation and a sagittal combined T1/T2 mapping for the quantification of cartilage composition.

Bone volume of the medial femoral condyle will be measured using previously validated methods. A single investigator experienced with quantitative and semi-quantitative assessments of knee MRIs⁴¹, will manually segment the medial femoral condyle on each slice of the MRI. Since the thickness of each slice is 3.5 mm, we will then calculate the medial condyle volume on each slice and then sum the volumes of all slices to generate the total medial condyle volume.

SECONDARY OBJECTIVES

Compare the change in patient-reported outcomes between patients treated with extended release triamcinolone acetonide or placebo following ACL reconstruction. The change in patient-reported outcomes (IKDC score, KOOSglobal score, and the Intermittent and Constant Osteoarthritis Pain (ICOAP) score) between the date of injection and the 6-month, 1-year, and 2-year postoperative follow-ups. The IKDC and KOOSglobal are knee-related patient-reported outcome tools. The IKDC has been validated in this specific patient population, and we developed and validated the KOOSglobal for use with young and potentially more active patient populations. The ICOAP was developed as part of the OARSI/OMERACT initiative and is a valid and reliable tool to assess OA-related pain.

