Therefore, these costs will be paid by the study:

- Knee aspirations performed at the time of surgery
- Pregnancy testing performed at Visit 3
- Administration of the study medication at Visit 3
- Limited physical examination performed at Visits 1, 3 and 4
- All questionnaires collected at Visits 3, 4, 5 and 6

The participant's insurance, Medicare, or Medicaid, may agree to pay for the costs. However, a co-payment or deductible may be needed.

Data and Safety Monitoring

The IRB requires review and approval of data and safety monitoring plans for greater than minimal risk research or NIH-funded/FDA-regulated clinical investigations.

- If you are conducting greater than minimal risk research, or your clinical investigation is NIH-funded, describe your Data and Safety Monitoring Plan (DSMP). [Click here for additional guidance on developing a Data and Safety Monitoring Plan.](#)
- If this is a non-sponsored investigator-initiated protocol considered greater than minimal risk research, and if you are planning on using a Data and Safety Monitoring Board (DSMB) as part of your DSMP, [click here for additional guidance](#) for information to include with your IRB application.

The DSMB is an independent multidisciplinary group with clinical research experience representing relevant specialties. This group will include a Research Subject Advocate (RSA) who is a Physician, a Pharmacist, an Internal Medicine Physician, Statistician, CCTS Representative and Executive Secretary. Ad-hoc members may be added when experience in specific disease areas or procedures is required.

The DSMB will meet tri-annually or as needed, and will review subject recruitment, AE's, side effects, withdrawals, protocol violations, and inclusion/exclusion criteria.

Future Use and Sharing of Research Data

If the results of this study will be used by members of the research team or shared with other researchers for future studies, please address the following:

- list the biological specimens and/or information that will be kept
- briefly describe the types, categories and/or purposes of the future research
- describe any risks of the additional use
- describe privacy/confidentiality protections that will be put into place
- describe the period of time specimens/information may be used
- describe procedures for sharing specimens/information with secondary researchers
- describe the process for, and limitations to, withdrawal of specimens/data

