Does your research fall under the purview of any of the other review committees listed below? *[If yes, check all that apply and attach applicable materials using the attachment button at the bottom of your screen.]*

Yes No

Additional Information

- Institutional Biosafety Committee
- Radiation Safety Committee
- Radioactive Drug Research Committee
- Markey Cancer Center (MCC) Protocol Review and Monitoring Committee (PRMC)
- Graduate Medical Education Committee (GME)
- Office of Medical Education (OME)

- [Institutional Biosafety Committee \(IBC\)](#) - Attach required IBC materials
- [Radiation Safety Committee \(RSC\)](#) - For applicability, see instructions and attach form
- [Radioactive Drug Research Committee \(RDRC\)](#)
- [Markey Cancer Center \(MCC\) Protocol Review and Monitoring Committee \(PRMC\)**](#) - Attach MCC PRMC materials, if any, per instructions.
- [Office of Medical Education \(OME\)](#)
- [Graduate Medical Education Committee \(GME\)](#)

Attachments

**** If your study involves cancer research, be sure to select "Cancer Research" in the "Research Attributes" section.** ORI will send your research protocol to the Markey Cancer Center (MCC) Protocol Review and Monitoring Committee (PRMC). The [MCC PRMC](#) is responsible for determining whether the study meets the National Cancer Institute (NCI) definition of a clinical trial and for issuing documentation to you (the investigator) which confirms either that PRMC approval has been obtained or that PRMC review is not required. Your IRB application will be processed and reviewed independently from the PRMC review.

53136 Statistical Analysis Plan:

Primary objective will be assessed using two-tailed independent t-tests for comparison between timepoints. Similarly, all secondary measures will be assessed using two-tailed independent t-tests.

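### One baseline-adjusted repeated-measures model per patient-reported outcome would be a cheap improvement on t-tests of change at 6 months, 1 year and 2 years

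*Combined protocol and SAP*

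**What the plan says.** The Secondary Objectives under Research Procedures name three instruments ("IKDC score, KOOSglobal score, and the Intermittent and Constant Osteoarthritis Pain (ICOAP) score") and define their change "between the date of injection and the 6-month, 1-year, and 2-year postoperative follow-ups". Costs to Subjects lists "All questionnaires collected at Visits 3, 4, 5 and 6". That is four occasions, which fits the injection visit plus three follow-ups.

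The Statistical Analysis Plan is two sentences long. For the secondary measures it says: "Similarly, all secondary measures will be assessed using two-tailed independent t-tests". It names no repeated-measures model, analysis population or missing-data rule, and neither does any other section.

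Other sections stop earlier. Hypothesis 2 in Study Design reads "Changes in patient reported-outcomes between eight and 6 months after surgery will be significantly greater", so it ends at 6 months. Background and the rest of Study Design collect the questionnaires at 8 weeks and 6 months only. The contraception criterion gives the participation period: "agreement to use such a method during study participation (18 weeks; 8 to 26 weeks after surgery".

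The Covariates section says that age, sex, race and BMI will be covariates in the statistical analyses. Its stated reason concerns biomarker concentrations, and it does not say whether the questionnaires are included.

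On retention, Subject Recruitment Methods & Advertising foresees withdrawal and missed visits. It limits payment to three visits: "Compensation will be mailed to the participant by check within two weeks after they have completed study visits 2, 3, and 4".

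**The concern.** A two-sample t-test on change to one visit uses only the patients seen at that visit. It does two things less well than it could.

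- It subtracts the baseline score with a fixed coefficient of one. When baseline and follow-up correlate only moderately, this adds noise that adjustment for baseline would remove.
- It discards what a patient reported at 6 months or 1 year if that patient is missing at 2 years. If the decision to stop answering depends on those earlier scores, and does so differently in the two arms, the patients left at 1 and 2 years are no longer a fair comparison.

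With 30 patients in total, a few lost questionnaires can move a 2-year result.

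**Working it through.** **1. The plan's own figures.** The sample size is a recruitment yield: 100 enrolled × 0.30 with persistent inflammation = 30, which agrees. The documents give no alpha, power, effect size, SD, correlation or dropout rate, so there is no planned precision to reproduce. The allocation ratio is not stated; I assume 1:1, so 30 / 2 = 15 per arm. If each follow-up is tested separately there are 3 instruments × 3 times = 9 comparisons.

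**2. Six months, everyone observed.** Take SD 1 and correlation ρ between baseline and follow-up.

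- Variance of the difference in mean change: 2 × 2(1 − ρ) / 15. At ρ = 0.5 this is 0.133, SD 0.365.
- Variance of the baseline-adjusted difference, ignoring the small cost of estimating the slope: 2(1 − ρ²) / 15. At ρ = 0.5 this is 0.100, SD 0.316.
- Ratio: 2 / (1 + ρ) = 1.33 at ρ = 0.5 and 1.18 at ρ = 0.7.

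A simulation of 3,000 trials per scenario, with equal correlation ρ between all visits and complete data, gave SDs of 0.360 and 0.317 at ρ = 0.5, ratio (0.360 / 0.317)² = 1.29. At ρ = 0.7 it gave 0.276 and 0.265, ratio 1.08. Without a baseline term the repeated-measures model and the t-test had identical SDs. With complete data, therefore, the whole gain comes from baseline adjustment.

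**3. Two years, random dropout (about 34% missing), same simulation.**

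| ρ | SD, t-test | SD, model without baseline | SD, model with baseline | Variance ratio, t-test to model without / with baseline |
|---|---|---|---|---|
| 0.5 | 0.458 | 0.445 | 0.410 | 1.06 / 1.25 |
| 0.7 | 0.359 | 0.345 | 0.336 | 1.08 / 1.14 |

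A second simulation let follow-ups correlate more strongly with each other (0.6 to 0.8) than with baseline (0.5), with 58 to 66% observed at 2 years. The ratio to the full model was 1.15 to 1.63, and baseline adjustment alone accounted for 1.22 to 1.32. In a further run with similar inputs, the repeated-measures part on its own contributed a factor of 0.89 to 1.29, so it does not always help precision.

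**4. Two years, dropout driven by earlier change.** In the first simulation the chance of leaving before 1 year was logistic(−1.2 − 1.5 × change at 6 months). Before 2 years it was half of the same function of change at 1 year. In the placebo-only scenario the active arm left at a constant rate instead. Bias of the 2-year difference, in SDs, at ρ = 0.5 and ρ = 0.7:

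| Dropout rule | True effect | t-test | Model with baseline |
|---|---|---|---|
| Same in both arms | 0 | 0.003, −0.006 | 0.003, −0.002 |
| Same in both arms | 0.8 | −0.101, −0.067 | −0.005, 0.007 |
| Placebo only | 0 | −0.214, −0.140 | −0.000, −0.007 |
| Placebo only | 0.8 | −0.220, −0.139 | 0.001, −0.003 |

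The second simulation used its own dropout rules. Its placebo-only bias was 0.06 to 0.17 SD for the t-test and at most 0.01 for the model. With a common rule, the t-test bias was 0.01 to 0.03 SD at a true effect of 0.6 and zero with no effect. The two sets differ because the rules are assumed. For scale, the sampling SD of the t-test estimate in the placebo-only rows above was 0.35 to 0.46.

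**The case against.** The strongest case on the other side has four parts.

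- **The plan does not say what is being criticised.** A reader might infer that it prespecifies three completer-only t-tests per instrument. It does not: the sentence on 6 months, 1 year and 2 years names no test, and several sections end at 6 months. This stands. Separate available-case tests are the natural reading of the two sections together, but whether the later changes are tested at all has to be settled first.
- **The model adds little at the time point that Hypothesis 2 uses.** This also stands in part. If dropout is monotone, the 6-month contrast comes from the same patients as the t-test, and the gain is baseline adjustment only. Patients with no follow-up score are left out either way.
- **A reader might infer that score-dependent dropout alone biases the t-test.** It does not. With the same rule in both arms and no treatment effect the bias is zero. Arm-specific dropout is an assumption, and nothing in this double-blind design points to it. A more extreme scenario, with opposite rules in the two arms, gave 0.27 to 0.55 SD; the documents offer no support for that either.
- **Heavy late loss is assumed.** Payment stops after Visit 4, which makes loss at Visits 5 and 6 plausible, but no rate is given.

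None of this favours the t-test. With complete data and no baseline term the two analyses agree, so little is risked by changing.

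**Conclusion.** This is a cheap improvement to the analysis of secondary outcomes; it does not show that the trial's conclusions would be wrong. The firmest part is baseline adjustment: the t-test on change has about 1.3 times the variance at 6 months if the correlation with baseline is 0.5, and less excess if the correlation is higher. At 2 years the ratio to a repeated-measures model is about 1.15 to 1.6, mostly for the same reason.

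Protection against bias at 1 and 2 years is a conditional benefit. It is worth about 0.06 to 0.17 SD in one assumed placebo-only scenario (0.14 to 0.22 under another rule). It is small with a common rule and a true effect (0.01 to 0.03 SD at an effect of 0.6; 0.07 to 0.10 at 0.8 under the other rule), and nil with a common rule and no effect. The model removes this bias only if dropout depends on scores already observed.

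All these sizes rest on assumed correlations, dropout rates and 1:1 allocation. Separately, the documents contradict themselves on how long the patient-reported outcomes are followed.

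**What to change.** For each of the three instruments, replace the t-tests with one likelihood-based repeated-measures model:

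- terms for arm, visit, arm-by-visit, baseline score and baseline-by-visit;
- every randomised patient with at least one follow-up score;
- unstructured covariance with Kenward-Roger degrees of freedom, and a simpler structure named in advance, such as compound symmetry, if it does not converge;
- the 6-month contrast for Hypothesis 2, with 1 and 2 years reported from the same model as supportive.

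Two reconciliations go with this. First, align the Secondary Objectives (to 2 years) and Costs to Subjects (Visits 5 and 6) with the inclusion criteria, Background and Study Design (to 6 months). If follow-up does end at 6 months, the model reduces to a baseline-adjusted comparison at that visit. Second, state whether the covariates in the Covariates section apply to these outcomes, because a plain t-test cannot include them.

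The cost is SAP wording and slightly more analysis work, with no new data or visits. With 30 patients, the fallback covariance may be needed.

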Patient will provide informed consent prior to undergoing ACL reconstruction with meniscal involvement. At the time of surgery, a knee aspiration will be performed in the operating room after the patient has been anesthetized so that synovial fluid can be collected. Synovial fluid samples will be assessed for the concentration of pro-inflammatory cytokine IL-1alpha. This will be done to identify patients that present with persistent inflammation after injury that may be at increased risk of cartilage degradation. Patients with elevated IL-1alpha, defined as synovial fluid concentrations ≥ 5 pg/mL, will then be randomized to one of two groups. The synovial fluid threshold of 5 pg/mL was based on our previously published study of ACL patients that demonstrated that those with elevated IL-1alpha at the time of surgery less likely to achieve a successful clinical outcome at 2 years (Latttermann et al., Biomed Res Int, 2018).

Eight weeks after surgery, the knee will be aspirated and one group will receive a single 32 mg Zilretta injection and the other group will receive a 5 mL saline injection. The syringes will be blinded to ensure that both the investigator administering the injection and the patient will be blinded to the group assignment. Patients will then be seen again six weeks later. Both prior to injection and at the 6-month follow-up visit, patients will undergo 3T MRI scans so that femoral shape can be assessed and will also be asked to complete patient-reported outcomes questionnaires and provide a urine sample.

Attachments

Subject Recruitment Methods & Advertising

Describe how the study team will identify and recruit subjects. Please consider the following items and provide additional information as needed so that the IRB can follow each step of the recruitment process.

- How will the study team identify potential participants?
- Who will first contact the potential subjects, and how?
- Will you use advertisements? If so, how will you distribute those?
- How and where will the research team meet with potential participants?
- If applicable, describe proposed outreach programs for recruiting women, minorities, or disparate populations.
- How you will minimize undue influence in recruitment?
- Attach copies of all recruiting and advertising materials (emails, verbal scripts, flyers, posts, messages, etc.).

For additional information on recruiting and advertising:

- [IRB Application Instructions - Advertisements](#)

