Determine if extended-release triamcinolone acetonide treatment alters the progression of cartilage degradation following ACL reconstruction. The change in a urinary biomarker of cartilage degradation (CTXII) between baseline and the 4-month postoperative follow-ups be compared between the treatment and placebo groups. Following cartilage degradation, CTXII (C-terminal crosslinked telopeptide type II collagen) is released into the synovial fluid, is circulated and then filtered by the kidneys. CTXII has been identified as a biomarker for the diagnosis, staging, and evaluating the prognosis of hip and knee OA, and has also been demonstrated to be responsive over short testing periods (3 months). We have reported that CTXII correlates with the degree of joint destruction and increases significantly within 1 month after ACL injury. CTXII will be measured in the urine by ELISA (Cartilaps® (CTX-II); Immunodiagnostic Systems, Inc, Fountain Hills, AZ) and will be normalized to creatinine levels (Quidel, San Diego, CA).

Biological data quality control: To ensure data quality and fidelity, all data collection and analysis procedures will be detailed in a structured manual. OA biomarker data collected will be carefully analyzed with respect to variability, linear range of standard, and need for repeat analyses. Controls provided with commercially available ELISA kits will be used with every run. For assays for which no control is available or provided, aliquots of serum from normal human subjects have been aliquoted and frozen at -80oC for this purpose. Each assay day, a fresh aliquot of this control serum is thawed and used on every plate to calculate intra- and inter-assay variance of the assay. In addition to the standard curve run in duplicate, this control will be run with each assay and the results used to determine the precision of the assay and to establish an acceptable control range for the assay. The mean of the control sample for all assays ± 2 standard deviations is defined as the acceptable control range. Any samples on a plate in which the control falls outside of this range will be excluded and repeated. Samples will be run in duplicate and reanalyzed if the coefficient of variation is $> 15\%$. For values that are below the level of detection, a value equivalent to 0.5 lowest limit of detection will be recorded and used for statistical analyses. Our team in Kentucky has used this methodology in prior works.

COVARIATES

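### No scale or baseline adjustment is specified for uCTX-II; the default t-test on raw change could lose about 7 to 31 points of power if the marker is log-normal

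*Combined protocol and SAP*

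**What the plan says.** Hypothesis 3 (Study Design) concerns "Changes in a urinary biomarker of cartilage breakdown (uCTXII) between eight and 6 months after surgery". Under Efficacy Assessments, Secondary Objectives, the comparison is described thus: "The change in a urinary biomarker of cartilage degradation (CTXII) between baseline and the 4-month postoperative follow-ups be compared between the treatment and placebo groups". The marker is measured in urine by ELISA and "will be normalized to creatinine levels". The biological data quality control paragraph adds that, for results below detection, "a value equivalent to 0.5 lowest limit of detection will be recorded and used for statistical analyses".

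The Statistical Analysis Plan is two sentences long. The one that governs this endpoint reads: "Similarly, all secondary measures will be assessed using two-tailed independent t-tests". No transformation, baseline adjustment, normality check, rank-based alternative or sensitivity analysis for substituted values appears in the documents. The quality control paragraph refers to a structured manual of procedures, which is not part of the material. The Covariates paragraph promises that age, sex, race and BMI will enter the analyses, which an independent t-test cannot do.

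On size, "This study will recruit a sample of 30 skeletally mature male and female participants", who "will then be randomized to one of two groups". The documents state no allocation ratio, significance level, effect size, SD or power for uCTX-II.

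**The concern.** Creatinine-normalised uCTX-II is a ratio of two positive quantities, so it is bounded at zero. Such a measure may well be right-skewed, with a treatment effect that acts proportionally. If it is, the raw change of a patient with a high baseline is large in absolute terms. A few such patients then dominate both the mean change and its variance. With about 15 patients per arm, that noise can hide a real effect.

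Hypothesis 3 rests on this single comparison, so the scale on which it is made matters. If the scale is not fixed before unblinding, it also remains a free choice after the data are seen.

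**Working it through.** **No figure to reproduce.** The plan gives no power or sample-size calculation for uCTX-II. For reference, 15 per arm with a two-sided 5% t-test has 80% power at a standardised difference of about 1.06.

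**Inputs.** From the documents: 30 patients, two groups, two-tailed independent t-test, change from baseline. Assumed: 1:1 allocation without dropout (15 per arm), 5% level, log-normal uCTX-II with log-SD s, correlation ρ between log baseline and log follow-up, and a multiplicative treatment effect r.

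**Formulas.** Standardised difference for each analysis:

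- Log change: |ln r| / (s√(2(1−ρ)))
- Log follow-up adjusted for log baseline: |ln r| / (s√(1−ρ²))
- Raw change, with baseline median set to 1: mean difference (1−r)e^(s²/2), divided by the root of the average of the two arms' change variances. With V = e^(s²)(e^(s²)−1) and C = e^(s²)(e^(ρs²)−1), those variances are 2V−2C (placebo) and V(1+r²)−2rC (active).

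**One case by hand: s = 0.4, ρ = 0.5, r = 0.7.**

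- Log change: 0.357/0.4 = 0.89.
- Adjusted log: 0.357/(0.4 × 0.866) = 1.03.
- Raw change: V = 0.2036 and C = 0.0977, so the variances are 0.2118 and 0.1666, with average 0.1892. The mean difference is 0.3 × 1.0833 = 0.325, and 0.325/√0.1892 = 0.75.

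The standardised difference therefore falls from 1.03 or 0.89 to 0.75.

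**Simulated power (%)**, 20,000 trials per row (standard error at most √(0.25/20,000), about 0.35 points), no values below detection:

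| r | s | ρ | Raw change | Log change | Log ANCOVA | Loss v log change | Loss v ANCOVA |
|---|---|---|---|---|---|---|---|
| 0.6 | 0.4 | 0.5 | 78.2 | 92.3 | 96.9 | 14.1 | 18.7 |
| 0.6 | 0.4 | 0.7 | 92.5 | 99.3 | 99.6 | 6.8 | 7.1 |
| 0.6 | 0.6 | 0.5 | 41.3 | 61.6 | 72.3 | 20.3 | 31.0 |
| 0.6 | 0.6 | 0.7 | 58.4 | 82.6 | 86.7 | 24.2 | 28.3 |
| 0.6 | 0.8 | 0.5 | 22.7 | 38.8 | 47.9 | 16.1 | 25.2 |
| 0.6 | 0.8 | 0.7 | 32.8 | 58.7 | 63.7 | 25.9 | 30.9 |
| 0.7 | 0.4 | 0.5 | 51.6 | 65.1 | 75.8 | 13.5 | 24.2 |
| 0.7 | 0.4 | 0.7 | 72.7 | 86.3 | 89.7 | 13.6 | 17.0 |
| 0.7 | 0.6 | 0.5 | 23.8 | 34.4 | 42.6 | 10.6 | 18.8 |
| 0.7 | 0.6 | 0.7 | 35.9 | 52.8 | 58.0 | 16.9 | 22.1 |
| 0.7 | 0.8 | 0.5 | 13.7 | 21.7 | 26.8 | 8.0 | 13.1 |
| 0.7 | 0.8 | 0.7 | 19.3 | 32.9 | 36.7 | 13.6 | 17.4 |

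A separate run of the sixth row gave 32.6 v 59.1, a loss of 26.5. The ranges are therefore about 7 to 27 points against log change and about 7 to 31 against ANCOVA.

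**Outside this grid.**

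- Smaller effect (r = 0.8, s = 0.4 to 1.0): the change-score loss is only about 3 to 9 points.
- Effect set for 80% log-change power, s = 0.3 to 1.0, ρ = 0.3 to 0.8: about 6 to 47 points.
- Near-normal data, additive effect, CV 0.20, 0.25 and 0.30: raw 79.9, 80.2 and 79.8; log 82.2, 81.6 and 79.9. The scales are within about 2 points.
- No treatment effect (r = 1) on the grid: the raw test rejects in 4.1% to 5.0% of trials.

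**Half-limit substitution**, effect set for 80% log-change power before substitution. At ρ = 0.5 the loss against log change is:

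| s | 0% below | 5% | 10% | 20% |
|---|---|---|---|---|
| 0.3 | 10.5 | 3.1 | 1.6 | 1.1 |
| 0.6 | 25.7 | 23.0 | 20.7 | 17.0 |

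At s = 0.3 and ρ = 0.7 to 0.8 with 10% to 20% below detection, raw change beats log change by about 2 to 7 points. At ρ = 0.8 it also beats the adjusted log analysis: 70.5 v 66.7 with 10% below, 65.1 v 63.1 with 20%. These runs apply the limit to the normalised value. That is a simplification, because the assay limit applies before division by creatinine.

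**The case against.** The plan never says raw scale. A t-test on log change is also an independent t-test, and the structured manual might settle the matter. This stands to the extent that raw change is the default reading of a silent plan and not its stated text. It does not remove the need to write the scale down before unblinding.

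The power figures assume log-normal values and a proportional effect, the conditions that favour the log scale by construction. That also stands: the grid shows the size of the loss if those conditions hold and is no evidence that they do. Near-normal data with an additive effect make the choice almost immaterial.

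Two stronger readings are tempting. A reader might infer that substituting half the detection limit is what damages the raw test. The calculations point the other way: it mainly hurts the log analysis. The documents also do not say that any uCTX-II value is expected below detection; the rule is a general one for the biomarker assays. A reader might also infer that a few high values can produce false positives. The raw test stays at or slightly under 5% when there is no effect, so only power is at issue.

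Finally, this is one secondary endpoint in a 30-patient Phase 2a trial. That limits the impact.

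**Conclusion.** The concern holds in a conditional form. As written, the plan leads by default to an unadjusted t-test on raw change in uCTX-II. Under the assumed log-normal, proportional-effect grid, this loses about 7 to 27 points of power against log change and about 7 to 31 against log-scale ANCOVA. No single figure can be taken from the documents, because they give no distribution, effect or correlation for this marker.

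The loss shrinks to about 3 to 9 points for a smaller effect. It nearly vanishes for near-normal data. It can reverse at low log-SD with high correlation and 10% to 20% of values below detection. The importance is moderate: the endpoint is secondary, but the remedy is almost free.

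**What to change.** In the SAP, name one governing uCTX-II analysis: ANCOVA of log(uCTX-II/creatinine) at follow-up on treatment and log baseline, reported as a ratio of geometric means with a 95% interval. Reconcile it with the Covariates paragraph by stating whether age, sex, race and BMI enter this model. Also reconcile the follow-up time, given as 4 months in the Secondary Objectives and 6 months in Hypothesis 3, so that the outcome is defined.

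Report the number below detection by arm and visit. Prespecify a rank-based or censored-data analysis as sensitivity only, so that the governing method does not depend on whether a value happened to be substituted.

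The cost is SAP wording; baseline and follow-up urine are already collected. There are two small downsides. The effect is expressed as a ratio and not a difference in concentration, and the log analysis is more sensitive to substituted values.
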